8.2 Statistical analysis of the secondary outcome variables

The secondary outcome variables will be summarized using descriptive statistics. All summary statistics will be presented overall and by dosing group and indication. A subgroup analysis will be performed for subjects with impaired hand function.

8.2.1 Proportion (%) of subject able to self-administer safe and effective injections at Visit 1

Safe and effective self-injection will be evaluated by the HCP at Visit 1 and is defined as:

- Complete Dose Delivery: Subject self-injected the complete dose of CZP as confirmed by a visual inspection of the CZP-cassette(s) which shows the PFS container to be empty and
- No AEs related to use of the e-Device (ADEs) that would preclude continued use of the e-Device for self-injection

For subjects with CD on the Q4W dosing regimen who will self-inject twice (2x200mg CZP) at each visit, each injection will be evaluated for safety and effectiveness using the above criteria. The endpoint of safe and effective self-injection for subjects on the Q4W dosing regimen will be met only if both self-injections are determined to be safe and effective at Visit 1.

The derivation of this secondary endpoint will follow the same algorithm as the derivation of the primary endpoint. No imputation of missing data will be performed.

The number and proportion (%) of subjects who meet the endpoint of safe and effective self-injection at Visit 1, as well as subjects who completed dose delivery, and subjects who has no AEs related to use of the e-Device will be summarized overall and by dosing group and indication. The number of subjects who administered the self-injection at Visit 1 will be used as the denominator to calculate the proportion (%). The corresponding 90% CI based on Exact Binomial method will also be presented.

8.2.2 Structural integrity of used CZP-cassettes

The trained site staff will inspect the used CZP-cassettes to determine if the used CZP-cassettes have structural integrity issues based on visual examination (ie, clear evidence of damage/compromised structural integrity, not superficial cosmetic imperfections). The assessment will be performed post each injection at Visit 1 and Visit 2.

The proportion (%) of cassettes with structural integrity issues will be summarized. The number of total cassettes will be used as the denominator to calculate the proportion (%). The corresponding 90% CI based on Exact Binomial method will also be presented.

8.3 Analysis of other outcome variables

The other outcome variables will be summarized using descriptive statistics. All other exploratory variables will be summarized overall and by dosing group and indication.

8.3.1 Injection site Pain (VAS)

A VAS will be used to assess overall injection pain due to self-injection at every visit during the Study Treatment Period. Subjects will be required to indicate their injection pain by placing a mark on a 100mm line from 0 (no pain) to 100 (worst possible pain). The VAS will be assessed immediately post injection (within 15 minutes). For subjects on the Q4W dosing regimen, the Pain VAS will record the overall pain associated with both self-injections.

Observed values of the injection site pain score at each visit will be summarized overall and by dosing group and indication using descriptive statistics.

8.3.2 Pre-injection ASI at Visit 1

The pre-injection ASI is composed of 6 items grouped into injections and self-confidence domains.

Domain score at Visit 1 will be summarized overall and by dosing group and indication using descriptive statistics. The domain score is calculated as the mean of the item scores included in the domain. Domain scores will be calculated only if at least half of the domain items are completed.

8.3.3 Post-injection ASI

The post-injection ASI is composed of 44 items grouped into 6 domains. The domains are feeling about injections, self-image, self-confidence, pain and skin reactions during and after injections, ease of use of the self-injection device, and satisfaction with self-injection.

Subjects on the Q4W dosing regimen who will self-inject twice (2×200mg CZP) at each visit will complete the post-injection ASI after the second injection at each of the 2 visits. For subjects on the Q4W dosing regimen, the post-injection ASI will collect the overall self-injection associated with both self-injections.

Domain scores at each visit will be summarized overall and by dosing group and indication using descriptive statistics. The domain score is calculated as the mean of the item scores included in the domain. Domain scores will be calculated only if at least half of the domain items are completed.

8.3.4 Self-injection preference questionnaire

The 9-item Self-Injection Preference Questionnaire was developed, based on patient input, to assess the self-injection experience and patient preference between the e-Device and PFS. The Self-Injection Preference Questionnaire will be completed by the subject at Visit 2 after the VAS. Subject response to each question will be summarized based on the following categories: ava®, your latest device, no preference. Responses will be summarized overall and by dosing group and indication using descriptive statistics.

8.3.5 Functional evaluation of the e-Device

The e-Device will also be evaluated for function integrity (ie, proper functioning) using a training cassette as specified in the in vitro e-Device functional testing directions.

The proportion (%) of e-devices found to be functionally compromised will be summarized. The corresponding 90% CI based on Exact Binomial method will also be presented.

9 PHARMACOKINETICS AND PHARMACODYNAMICS

9.1 Pharmacokinetics

Not applicable.

9.2 Pharmacodynamics

Not applicable.

10 SAFETY ANALYSES

All safety summaries and listings will be performed using all subjects in the SS.

10.1 Extent of exposure

The duration of exposure (in days) for Q2W group will be calculated as:

$$\text{Duration of exposure} = \text{Date of last injection} - \text{Date of first injection} + 14$$

14 days refer to the treatment period of Q2W regimen.

The duration of exposure (in days) for Q4W group will be calculated as:

$$\text{Duration of exposure} = \text{Date of last injection} - \text{Date of first injection} + 28$$

28 days refer to the treatment period of Q4W regimen.

For subjects who die during the study, the duration of exposure (in days) will be calculated as:

$$\text{Duration of exposure} = \text{Date of death} - \text{Date of first injection} + 1$$

for both Q2W and Q4W.

The duration of exposure will be summarized overall and by dosing group and indication using descriptive statistics. A listing of data of first and last self-injection with e-Device will be provided.

10.2 Adverse events

10.2.1 Adverse event (IMP)

An adverse event (AE) is any untoward medical occurrence in a patient or clinical investigation subject administered a pharmaceutical product that does not necessarily have a causal relationship with this treatment. An AE can therefore be any unfavorable and unintended sign (including an abnormal laboratory finding), symptom, or disease temporally associated with the

use of a medicinal (investigational) product, whether or not related to the medicinal (investigational) product.

In this study, safety reporting requirements apply to all constituents of the IP (including CZP, the e-Device auto-injector, and the CZP-cassette) per 21 CFR 320. Adverse events related to use of the e-Device (ADEs) (including the CZP-cassette) will be summarized separately. Adverse events will be summarized by the frequency and percent of subjects having one or more of the events in question. Planned summaries include overall AEs, AEs by intensity, AEs by relationship to study drug, SAEs, AEs leading to withdrawal, AEs leading to death, ADEs, SADEs, and AEs of special interest.

Treatment-emergent AEs (TEAE) will be summarized overall and by dosing group and indication. Treatment-emergent AEs (TEAE) are those with onset date at or after the first self-injection with the e-Device up to 70 days after the last self-administration of study medication with the e-Device.

The incidence of TEAEs will be summarized by MedDRA SOC, high level term, and PT. Tables with incidences of classified TEAEs by maximum intensity, by relationship, and by subject number will be provided. Furthermore, the incidence of all TEAEs, serious TEAEs, TEAEs leading to study discontinuation and/or permanent withdrawal of study medication, TEAEs leading to death, and AE of special interest will be summarized. In addition, an overall summary table will be provided.

For each AE the following information will be listed for the SS: AE term (verbatim term), date of onset, pattern of event, whether or not the AE was classified as a SAE, as an AE of special interest, intensity, relationship to study medication, relationship to study device, action taken with study medication, other action taken, outcome, date of outcome, and whether the AE led to study drug discontinuation or to study discontinuation.

TEAEs with incidence of above reporting threshold of 5% of subjects will be summarized.

For all TEAEs the following variables will be calculated:

- Duration
- Time since first injection

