5.1.1 Study duration per subject

The study duration for each subject in the Q2W group on the Q2W dosing regimen is 3 weeks. The study duration for each subject in the Q4W group on the Q4W dosing regimen is 5 weeks.

Subjects will be required to perform a Safety Follow-Up by phone 1 week after their last study dose of CZP. Subjects who have a positive pregnancy test and who have self-administered at least 1 study dose of CZP who then discontinue CZP therapy will have a safety follow-up telephone call 70 days after the last study dose of CZP in addition to the 1-week Safety Follow-Up.

The end of the study is defined as the date of the last telephone follow-up call for the last subject in the study.

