8.4 Safety Follow-Up

A Safety Follow-Up by telephone will be conducted 1 week after the subject's final site visit using the e-Device. Any AEs or ADEs will be recorded.

Subjects who are withdrawn from CZP treatment during the course of the study due to pregnancy will be required to perform a safety follow-up telephone call 70 days following their final CZP administration in addition to the 1-week Safety Follow-Up.

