For both groups, a follow-up telephone call will be conducted 1 week after the final study drug administration as a safety follow-up call. Follow-up requirements for adverse events (Investigational Medicinal Product (IMP) and investigational device) and pregnancy are outlined in the protocol Sections 10.1.3, 10.2.3, and 10.3. Subjects who have a positive pregnancy test and who have self-administered at least 1 study dose of CZP who then discontinue CZP therapy will have a safety follow-up telephone call 70 days after the last study dose of CZP in addition to the 1-week Safety Follow-Up.

The study duration for each subject in the Q2W group on the Q2W dosing regimen is 3 weeks. The study duration for each subject in the Q4W group on the Q4W dosing regimen is 5 weeks.

Subjects will be required to perform a Safety Follow-Up by phone 1 week after their last study dose of CZP. Subjects who have a positive pregnancy test and who have self-administered at least 1 study dose of CZP who then discontinue CZP therapy will have a safety follow-up telephone call 70 days after the last study dose of CZP in addition to the 1-week Safety Follow-Up.

The end of study is defined as the date of the last telephone follow-up call for the last subject in the study.

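### TEAE percentages are tabulated by dosing group and indication although scheduled adverse event follow-up is 21 days in Q2W and 35 days in Q4W, and nothing in the tables accounts for the difference

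*SAP*

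**What the plan says.** SAP 10.2.1 fixes the measure, "Adverse events will be summarized by the frequency and percent of subjects having one or more of the events in question", and the layout, "Treatment-emergent AEs (TEAE) will be summarized overall and by dosing group and indication".

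Follow-up differs by regimen. Protocol 5.1.1 states "The study duration for each subject in the Q2W group on the Q2W dosing regimen is 3 weeks" and "The study duration for each subject in the Q4W group on the Q4W dosing regimen is 5 weeks". In both groups the last routine contact is the same short step after dosing (SAP 2.3): "Subjects will be required to perform a Safety Follow-Up by phone 1 week after their last study dose of CZP". SAP section 2 places every Crohn's disease subject on Q4W, while RA, PsA and AS subjects may be on either schedule. The split is not given.

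Two other clocks appear. TEAEs count "up to 70 days after the last self-administration of study medication with the e-Device", but under Protocol 8.4 the 70-day call is only for subjects withdrawn because of pregnancy. SAP 10.1 defines exposure as the time between first and last injection plus 14 days (Q2W) or 28 days (Q4W).

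SAP 10.2 plans no rate per unit of observation time, no common time window and no caution about unequal follow-up. SAP 3.1 makes all analyses descriptive.

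**The concern.** A percentage of subjects with at least one event rises with the time over which events are asked about. When columns with different follow-up stand next to each other, part of any difference between them reflects the calendar. Here the longer follow-up coincides with Q4W and with Crohn's disease, the columns in which a reader might look for a regimen or population effect.

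The documents recognise the difference in treatment period and give it as one reason to evaluate the two groups separately, but they do not carry it into the TEAE tables. The by-indication and overall columns can mix 21-day and 35-day subjects. At stake is the interpretation of background events, meaning those unrelated to the injection, in the safety tables.

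**Working it through.** **Planned follow-up, reproduced.** Visit interval plus one week: 14 + 7 = 21 days (Q2W) and 28 + 7 = 35 days (Q4W). These match the stated 3 and 5 weeks. The ratio is 35/21 = 1.67.

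**Effect on percentages.** Assume completers at nominal visit times and one constant background hazard in both groups. If p is the 21-day incidence, the 35-day incidence is P = 1 − (1 − p)^(35/21). The documents give no background incidence, so p is an assumption and a range is shown.

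| Q2W, 21 days (p) | Q4W, 35 days (P) | Ratio P/p |
|---|---|---|
| 1% | 1.7% | 1.66 |
| 5% | 8.2% | 1.64 |
| 10% | 16.1% | 1.61 |
| 20% | 31.1% | 1.55 |
| 30% | 44.8% | 1.49 |
| 50% | 68.5% | 1.37 |

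**Crohn's disease against another indication.** If a share q of that indication is on Q4W, the low-incidence ratio is 35 / [21(1 − q) + 35q]. This gives 1.67 at q = 0, 1.43 at q = 0.25, 1.25 at q = 0.5 and 1.00 at q = 1.

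**The 70-day window.** If ascertainment were complete to 70 days after the last dose, the windows would be 14 + 70 = 84 and 28 + 70 = 98 days, and the ratio at most 98/84 = 1.17. No routine contact is planned in that period, so 21 and 35 days describe the scheduled ascertainment.

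**Chance.** Assume 30 subjects per group and daily hazards of 0.002, 0.005, 0.01 and 0.02. The expected percentages are then 4.1 vs 6.8, 10.0 vs 16.1, 18.9 vs 29.5 and 34.3 vs 50.3. The probability that the observed Q4W percentage exceeds the Q2W percentage is 56%, 70%, 79% and 87%. The exact 90% confidence interval for 3/30 runs from 2.8% to 23.9%, which contains 16.1%.

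**SAP 10.1 exposure as a possible denominator.** It credits 14 + 14 = 28 days and 28 + 28 = 56 days. Scheduled follow-up covers 21/28 = 75% and 35/56 = 62.5% of these. At equal hazards, events per exposure day would have a ratio of 0.625/0.75 = 0.83 instead of 1.

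**With time at risk as denominator.** Take p = 10%. The daily hazard is −ln(0.9)/21 = 0.00502. Mean time to first event or end of follow-up is 0.100/0.00502 = 19.9 days in Q2W and 0.161/0.00502 = 32.1 days in Q4W. Both groups then show 0.50 first events per 100 subject-days, a ratio of 1.00.

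**The case against.** The strongest reply is that the plan does not invite the comparison. It says the two groups are evaluated separately because their treatment periods differ, it is descriptive throughout, and it presents no p-values. Percent of subjects with an event is a usual display, and nominal follow-up is the same for everyone within a dosing group. Study duration is stated, exposure is summarised in the same columns, visit dates are listed, and time since first injection is calculated for each TEAE. Adverse device effects are summarised separately. All of this stands and limits the weight of the point. It does not remove it, because the columns still appear in the same summaries and the by-indication columns can cut across regimens.

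Four stronger readings are not supported:

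- A reader might infer that Crohn's disease must look 1.6 times worse than the other indications. That holds only against Q2W subjects. If indication is shown within dosing group, Crohn's disease and other Q4W subjects have equal follow-up.
- A reader might infer that the tables will certainly show more events in Q4W. At this sample size it is a tendency.
- A reader might take exposure to be the only time measure planned. Time since first injection is planned too.
- A reader might charge the SAP with the 0.83 ratio. It never divides adverse events by exposure, so this is only a caution for choosing a denominator.

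**Conclusion.** The point holds in a limited form. TEAE percentages are set out by group and indication over unequal follow-up, and nothing in the planned tables says so or allows for it. At an equal, constant background hazard the expected Q4W to Q2W ratio is about 1.6 for uncommon events, falling to about 1.5 and 1.4 at 21-day incidences of 30% and 50%. For Crohn's disease against RA, PsA or AS these figures are upper bounds.

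The result rests on nominal visit times, completers and a constant hazard. Events clustered around the two dosing visits, which both groups have, would lower the ratio, and so would capture of events after the one-week call. The primary outcome and its intervals are untouched. With as few as 15 subjects in a group, chance may exceed the effect. This is a low-cost improvement to how descriptive safety tables read, not a flaw that undermines the study.

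**What to change.** In SAP 10.2.1, for the TEAE overview by dosing group and indication:

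- Footnote that planned adverse event observation is 21 days in Q2W and 35 days in Q4W.
- Add total adverse event observation time, and subjects with a first TEAE per 100 subject-days at risk. Counting subjects, not events, avoids counting one event twice, since Protocol 10.1.2.2 has a worsened event reported again.
- Define time at risk as running from the first e-Device injection to the earliest of first TEAE, the Safety Follow-Up contact, or the last contact if there was no follow-up call.
- Count in this rate only TEAEs with onset within that period. List later TEAEs, up to 70 days after the last dose, separately, so that numerator and denominator cover the same time.
- Do not use SAP 10.1 exposure as the denominator.

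The planned percentages stay as they are. Injection and visit dates are already collected and listed. The cost is a slightly longer table and a small amount of extra programming.

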10.2.2 Adverse device effect (investigation device)

An adverse device effect (ADE) is an AE related to the use of an investigational device.

The incidence of ADEs and serious ADEs will be summarized separately by MedDRA SOC, high level term, and PT. Each ADE will be listed for the SS.

10.2.3 AE of special interest

AEs of interest will be summarized. The following AEs of interest will be summarized in stand-alone tables:

- Opportunistic infections
- Malignant and unspecified tumors
- Malignant tumors
- Serious cardiovascular events

- Aplastic anemia, pancytopenia, thrombocytopenia, neutropenia, and leucopenia
- Serious bleeding events
- Demyelinating-like disorders

For the following AEs of interest, no additional tables will be provided, as these are included in the standard AE summaries:

- Serious infections
- Congestive heart failure
- Lupus and lupus-like illness
- Serious skin reactions (eg, Stevens Johnson Syndrome, toxic epidermal necrosis, and erythema multiforme)

The following events are not officially considered to be AEs of interest but are nonetheless considered to be interesting enough to be summarized in stand-alone tables: 1) Hepatic events and 2) Hypersensitivity reactions and anaphylactic reactions.

Potential Hy's Law, defined as $\geq 3 \times \text{ULN}$ alanine aminotransferase or aspartate aminotransferase with coexisting $\geq 2 \times \text{ULN}$ total bilirubin in the absence of $\geq 2 \times \text{ULN}$ alkaline phosphatase, with no alternative explanation for the biochemical abnormality will also be summarized.

The approach for summarizing AEs of interest is detailed in the UCB AE of interest program specifications for Cimzia.

10.3 Vital signs

Vital signs will include systolic and diastolic blood pressure (BP), pulse, respiratory rate (RR), and body temperature. Vital signs will be measured at Visit 1 and Visit 2.

Vital signs will be summarized overall and by dosing group and indication using descriptive statistics and frequency tabulations. Summary statistics of vital sign values and change from baseline will be presented at each scheduled visit.

Temperature measurements will only be listed and not summarized in a table.

10.4 Physical examination

Physical examination abnormalities will be recorded in the eCRF only at Screening. Clinically relevant changes in subsequent physical examinations will be recorded as AEs. Physical examination findings at Screening will be listed.

STATISTICAL ANALYSIS PLAN SIGNATURE PAGE

This document has been reviewed and approved per the Review and Approval of Clinical Documents Standard Operating Procedures. Signatures indicate that the final version of the Statistical Analysis Plan (SAP) or amended SAP is released for execution.

REDACTED COPY
This document cannot be used to support any marketing authorization application and any extensions or variations thereof.

RA0098 Statistical Analysis Plan

ELECTRONIC SIGNATURES

Signed by	Meaning of Signature	Server Approval Date (dd-mon-yyyy (HH:mm))
[REDACTED]	Clinical Approval	20-Nov-2017 10:29 GMT+0
[REDACTED]	Clinical Approval	20-Nov-2017 14:33 GMT+0
[REDACTED]	Clinical Approval	20-Nov-2017 15:11 GMT+0

This document cannot be used to support any marketing authorization application and any extensions or variations thereof.
REDACTED COPY
